3.4 Exploratory Objectives

- To evaluate soluble PD-L1, circulating cytokines and immune profiling, before, during, and after therapy with pembrolizumab and their relationship to clinical outcome. Given that these assays are still being optimized and we don't know what pattern of circulating factors will be observed in SCLC (for instance, 5 different isoforms of soluble PD-L1 are seen in melanoma, [name], personal communication), descriptive statistics will be used for assessment of serial measures of circulating markers.

- To evaluate gene expression using nanostring and tumor genotype using next-generation sequencing and whole-exome sequencing (WES) and determine relationship, if any, to clinical benefit with pembrolizumab (WES will be performed on a subset of samples if tissue is available). Again, given unknown findings for SCLC, descriptive statistics will be used to assess relationship of mutational pattern to outcome.

4 Subject Selection and Withdrawal

Participants will include patients with extensive-stage small cell lung cancer undergoing standard treatment with platinum-etoposide combination chemotherapy. One cohort of participants will be enrolled PRIOR to the start of chemotherapy and receive pembrolizumab along with chemotherapy from the start of therapy (cohort A). A second cohort of participants will be eligible to enroll after 1 prior cycle of chemotherapy (cohort B) and will receive pembrolizumab along with continued chemotherapy. A third cohort will be eligible to enroll after completion of 1st line chemotherapy (cohort C) and will receive pembrolizumab as maintenance therapy. A fourth cohort will be eligible to enroll after completion of consolidation thoracic radiation (cohort D) and will receive pembrolizumab as maintenance therapy.

4.1 Eligibility/Inclusion Criteria

1. Participants must have histologically confirmed small cell lung carcinoma not amenable to initial concurrent radiotherapy (extensive-stage disease).
2. Participants may have evaluable or measurable disease, defined as at least one lesion that can be accurately measured in at least one dimension (longest diameter to be recorded for non-nodal lesions and short axis for nodal lesions) as ≥ 20 mm with conventional techniques or as ≥ 10 mm with spiral CT scan, MRI, or calipers by clinical exam. See Section 7.0 for the evaluation of measurable disease.
3. Participants in cohort B must have completed 1 cycle of systemic chemotherapy. Therapy with the combination must start no sooner than 3 weeks from the last dose of chemotherapy and no later than 5 weeks from the last dose of chemotherapy. Participants in cohort B must not have had progression of disease prior to the start of therapy.
4. Participants in cohort C must have completed systemic therapy (4-6 cycles cisplatin or carboplatin + etoposides) and NOT be a candidate for consolidation thoracic radiotherapy or PCI. Participants in cohort C must initiate therapy with pembrolizumab within 6 weeks of the last dose of chemotherapy (therapy must not start within 2 weeks from the last dose). Participants in cohort C must not have had progression of disease prior to the start of therapy.
5. Participants in cohort D must have completed systemic therapy AND have completed either consolidation thoracic radiotherapy or PCI or both completed either consolidation thoracic radiotherapy or PCI or both. Participants in cohort D must initiate therapy with pembrolizumab within 6 weeks of the last dose of radiation. Therapy must not start within 2 weeks from the

last dose. **Consolidation radiotherapy dose must NOT be more than 3000 cGy.**
 Participants in cohort D must not have had progression of disease prior to the start of therapy.

6. Age > 18 years.
7. ECOG performance status ≤ 2 (Karnofsky $\geq 60\%$, see Appendix A)
8. Life expectancy of greater than 3 months.
9. Participants must have normal organ and marrow function during screening and on Cycle 1, day 1 as defined below:

Table 1 Adequate Organ Function Laboratory Values

System	Laboratory Value
Hematological	
Absolute neutrophil count (ANC)	$\geq 1,500$ /mcL
Platelets	$\geq 100,000$ / mcL
Hemoglobin	≥ 9 g/dL or ≥ 5.6 mmol/L without transfusion or EPO dependency (within 7 days of assessment)
Renal	
Serum creatinine OR Measured or calculated ^a creatinine clearance (GFR can also be used in place of creatinine or CrCl)	≤ 1.5 X upper limit of normal (ULN) OR ≥ 60 mL/min for subject with creatinine levels > 1.5 X institutional ULN
Hepatic	
Serum total bilirubin	≤ 1.5 X ULN OR Direct bilirubin \leq ULN for subjects with total bilirubin levels > 1.5 ULN
AST (SGOT) and ALT (SGPT)	≤ 2.5 X ULN OR ≤ 5 X ULN for subjects with liver metastases
Albumin	≥ 2.5 mg/dL
Coagulation	
International Normalized Ratio (INR) or Prothrombin Time (PT)	≤ 1.5 X ULN unless subject is receiving anticoagulant therapy as long as PT or PTT is within therapeutic range of intended use of anticoagulants
Activated Partial Thromboplastin Time (aPTT)	≤ 1.5 X ULN unless subject is receiving anticoagulant therapy as long as PT or PTT is within therapeutic range of intended use of anticoagulants
^a Creatinine clearance should be calculated per institutional standard.	

10. Availability of a diagnostic or pre-chemotherapy tissue biopsy is required (cytologic specimens or bone biopsies not accepted). This biopsy must be within 6 weeks of starting initial therapy. A minimum of 20 5 µm slides or block is required.
11. Participants in cohorts B-D must be willing to provide tissue from a newly obtained core or excisional biopsy of a tumor lesion. Newly-obtained is defined as a specimen within 4 weeks to initiation of treatment and AFTER the last dose of any prior therapy.
12. Participants with treated brain metastases are allowed. Radiation must be completed at least 2 weeks prior to pembrolizumab dosing and participants must not require ongoing steroids. Participants with untreated brain metastases that are all <5 mm with no clinical symptoms or vasogenic edema may be allowed on study on a case-by-case basis on discussion with sponsor. These participants will require MRI monitoring every 6 weeks to ensure stability.
13. The effects of pembrolizumab on the developing human fetus are unknown. For this reason and because the chemotherapy and radiation also used in this trial are known to be teratogenic, women of child-bearing potential and men must agree to use adequate contraception (hormonal or barrier method of birth control; abstinence) or be surgically sterile prior to study entry and for the duration of study participation. Subjects of childbearing potential are those who have not been surgically sterilized or have not been free from menses for > 1 year. Should a woman become pregnant or suspect she is pregnant while she or her partner is participating in this study, she should inform her treating physician immediately.
14. Men treated or enrolled on this protocol must also agree to use adequate contraception prior to the study, for the duration of study participation, and 4 months after completion of chemotherapy, radiation, and pembrolizumab administration.
15. Ability to understand and the willingness to sign a written informed consent document.

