1. RATIONALE

SCLC provides an opportune setting to evaluate the potential importance of variability in PD-L1 expression and its influence on optimizing timing and efficacy of checkpoint inhibition. All extensive-stage SCLC patients are treated with chemotherapy and recent data suggests added benefit to consolidation thoracic radiation¹⁰. A prior study of patients with known PD-L1 expression showed a 35% response rate. That study used archival specimens and found a 29% PD-L1 positivity rate (at 1% level) suggesting that the expression level and prevalence could be higher (and response rate/outcome therefore potentially better) in patients who have previously had chemotherapy or radiation.

The proposed study seeks to evaluate pembrolizumab therapy initiated at different times during the course of SCLC treatment: a) up front, in conjunction with initiation of chemotherapy, b) starting after one cycle of chemotherapy, c) starting after completion of 1st line chemotherapy (4-6 cycles), d) starting after completion of consolidation thoracic radiation therapy and/or PCI. Treatment with pembrolizumab will be preceded by biopsy for evaluation of PD-L1 expression with correlative evaluation of changes in PD-L1 expression (relative to diagnostic biopsy) and changes in other tissue- and blood-based biomarkers and immune markers.

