3. TREATMENT PLAN

Each cohort will consist of 15 patients. All patients will be treated with up to 6 cycles of cis/carboplatin + etoposide. Eligible patients for consolidation thoracic radiotherapy will complete this within 6 weeks following completion of chemotherapy. All patients will be required to have pre-treatment biopsies prior to initiation of pembrolizumab for evaluation of PD-L1 expression and other correlative evaluations (within 4 weeks of start). Cohorts B-D will ALSO be required to submit a diagnostic biopsy specimen (prior to any treatment) for intra-subject comparison of PD-L1 expression between biopsies.

Cohort A will start pembrolizumab at the same time as starting standard chemotherapy with carboplatin + etoposide and receive all three drugs. Cohort B will start pembrolizumab after one cycle of cis/carboplatin/etoposide and receive all three drugs for the remaining cycles. Cohort C will consist of subjects who are not candidates for consolidation thoracic radiotherapy (thoracic RT) or prophylactic cranial irradiation (PCI) but who have completed 1st line therapy with 4-6 cycles of chemotherapy—these subjects will start pembrolizumab after completion of chemotherapy. Cohort D will consist of patients who have completed 4-6 cycles of carboplatin + etoposide as well as consolidation thoracic radiotherapy and/or PCI—these subjects will start pembrolizumab after completion of chemotherapy and radiation.

Pembrolizumab will be continued until progression following completion of standard treatment for all cohorts or for up to 2 years of therapy total.

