6. CORRELATIVE STUDIES

Diagnostic biopsy specimens (20 slides) from all participants will be evaluated for PD-L1 expression on tumor cells as well as within the tumor microenvironment. For cohorts B-D, an additional mandatory biopsy specimen will also be evaluated and compared to the diagnostic biopsy specimen. Optional post-treatment biopsies will also be collected. All tumor specimens will be evaluated for PD-L1, CD3, FOXP3, TIM3, LAG3 and other immune biomarkers if sufficient tissue available. Next-gen sequencing-based genotyping and gene expression profiling using nanostring will be performed from pre-treatment biopsies from all participants. A subset who have fresh tissue samples collected will also have immune profiling and whole-exome sequencing performed. All participants will have blood samples collected pre, during, and post-treatment for evaluation of soluble PD-L1 and cytokine profiling as well as possible sequencing.

SCHEMA

Pembrolizumab therapy starts at different time points for each cohort

- A) concurrent with cycle 1 chemotherapy
- B) after cycle 1 (concurrent therapy)
- C) after completion of 4-6 cycles of chemotherapy (maintenance monotherapy)
- D) after thoracic radiation+/- prophylactic cranial irradiation (maintenance monotherapy)

Biopsies:

- a) Cohort A will have single required diagnostic biopsy
- b) Cohort B will have diagnostic biopsy and required pre-treatment with pembrolizumab biopsy (after cycle 1 chemotherapy)
- c) Cohort C will have diagnostic biopsy and required pre-treatment with pembrolizumab biopsy (after completion of 4-6 cycles chemotherapy)
- d) Cohort D will have diagnostic biopsy and required pre-treatment with pembrolizumab biopsy (after completion of chemotherapy and radiation).

Core biopsy prior to pembrolizumab required for all cohorts in addition to diagnostic biopsy for cohorts B-D (Diagnostic biopsy must be core or greater to allow for paired biopsy comparisons).

1 Introduction

This document is a protocol for a human research study. This study is to be conducted in accordance with US government research regulations, and applicable international standards of Good Clinical Practice, and institutional research policies and procedures.

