SCLC provides an opportune setting to evaluate the potential importance of variability in PD-L1 expression and its influence on optimizing timing of checkpoint inhibition. All extensive-stage SCLC patients are treated with chemotherapy and recent data suggests added benefit to consolidation thoracic radiation¹⁰. A prior study of patients with known PD-L1 expression showed a 35% response rate. That study used archival specimens and found a 29% PD-L1 positivity rate (at 1% level) suggesting that the expression level and prevalence could be higher (and response rate/outcome therefore potentially better) in patients who have previously had chemotherapy or radiation.

The proposed study seeks to evaluate pembrolizumab therapy initiated at different times during the course of SCLC treatment: a) up front, in conjunction with initiation of chemotherapy, b) starting after two cycles of chemotherapy, c) starting after completion of 1st line chemotherapy, d) starting after completion of consolidation thoracic radiation therapy. Treatment with pembrolizumab will be preceded by biopsy for evaluation of PD-L1 expression with correlative evaluation of changes in PD-L1

expression (relative to diagnostic biopsy) and changes in other tissue- and blood-based biomarkers and immune markers.

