2.1 Primary Objectives

Primary Objective:

- To determine PD-L1 expression status in subjects with SCLC and assess changes in expression following chemotherapy and radiation in pre-specified cohorts of SCLC.
 - A—subjects who are chemotherapy and radiation naïve
 - B—subjects who have had 1 prior cycle of 1st line chemotherapy with cisplatin or carboplatin + etoposide for extensive-stage SCLC
 - C—subjects who have completed 4-6 cycles of chemotherapy with cisplatin/carboplatin + etoposide and are not going to receive further radiation therapy
 - D—subjects who have completed 4-6 cycles of cisplatin/carboplatin + etoposide and consolidation thoracic radiation therapy (with or without the addition of prophylactic cranial irradiation)

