3.1 General Design

This is a phase II study of pembrolizumab therapy initiated at different times during the course of SCLC treatment: **a)** up front, in conjunction with initiation of chemotherapy, **b)** starting after one cycle of chemotherapy, **c)** starting after completion of 1st line chemotherapy, and **d)** starting after completion of consolidation thoracic radiation therapy.

Treatment with pembrolizumab will be preceded by biopsy for evaluation of PD-L1 expression at baseline prior to any treatment (cohort A); after short-term exposure to chemotherapy (cohort B); after completion of chemotherapy (cohort C, which will include both patients with chemotherapy-sensitive disease (stable/continued response) and those with chemotherapy-refractory disease (progression within 60 days of completion of treatment with carboplatin-etoposide); and after exposure to radiation therapy (cohort D). These timed biopsies will permit correlative evaluation of changes in PD-L1 expression (relative to diagnostic biopsy) and changes in other tissue and blood based immune markers before, during, and after therapy.

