FOR COHORTS A AND B ONLY: Initial enrollment will include only 3 participants, who may be enrolled into either cohort A or B. Once these three participants have cleared cycle 1, an additional 3 participants may be enrolled into either cohort A or B if no DLTs are seen. If < 2 DLTs are seen in the first 6 participants, enrollment to the rest of the cohorts will proceed. If ≥ 2 DLTs are seen, enrollment will be halted and discussion of dosing change with Merck and the overall PI will occur prior to further enrollment. Based on safety data to date with other platinum-based regimens, we do not anticipate interactions that would necessitate dosing change, so there will not be pre-specified dose reductions planned. Cohorts A and B will be pooled for the purposes of DLT evaluation as the treatment regimen after study initiation is identical.

Cohort C: participants will have previously received 4-6 cycles of platinum-based therapy and have stable disease. In addition, these patients must not be candidates for further consolidation thoracic radiotherapy or PCI. Pembrolizumab treatment should start no sooner than 2 weeks and no later than 6 weeks from the start of the last cycle of chemotherapy. Therapy will continue for up to 34 cycles (2 years).

Cohort D: participants will have previously received 4-6 cycles of platinum-based chemotherapy and thoracic radiation therapy or PCI or both. Pembrolizumab treatment should start no sooner than 2 weeks and no later than 6 weeks from the start of the last dose of radiation. Therapy will continue for up to 34 cycles (2 years).

Treatment will be administered on an outpatient basis. Reported adverse events and potential risks are described in Section 1.8.1. Appropriate dose modifications are described in Section 5. No investigational or commercial agents or therapies other than those described below may be administered with the intent to treat the participant's malignancy.

All patients will be required to have a tissue biopsy within 3 weeks of study entry and after completion of prior therapy (see section 6.6.7.1). For cohort A, this time frame could be up to 6 weeks.

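### Cohort D is thoracic radiation in the primary objective but may be cranial irradiation alone in eligibility, and un-irradiated tumour is pooled with irradiated tumour in one paired analysis

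*Combined protocol and SAP*

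**What the plan says.** Cohort D is defined in two ways.

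- **Thoracic radiation required.** Section 2.1 (Primary Objectives) asks for 4-6 cycles of platinum-etoposide plus "consolidation thoracic radiation therapy (with or without the addition of prophylactic cranial irradiation"). The schema agrees: "after thoracic radiation+/- prophylactic cranial irradiation (maintenance monotherapy").
- **PCI alone sufficient.** Section 4.1 item 5 states "Participants in cohort D must have completed systemic therapy AND have completed either consolidation thoracic radiotherapy or PCI or both". Section 5.3 states "participants will have previously received 4-6 cycles of platinum-based chemotherapy and thoracic radiation therapy or PCI or both". The synopsis Rationale has "starting after completion of consolidation thoracic radiation therapy and/or PCI", wording that the opening of section 9 repeats. The synopsis Treatment Plan has "as well as consolidation thoracic radiotherapy and/or PCI".

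A third group does not settle the matter. Section 1.6, section 3.1 ("starting after completion of consolidation thoracic radiation therapy") and the introduction to section 4 name thoracic radiation and are silent on PCI alone. Sections 1.7 and 6.7.1.1 say only that radiotherapy was completed.

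For the new biopsy, section 4.1 item 11 asks for a core or excisional sample of a tumour lesion. Sections 6.6.7.1 and 6.7.1.2 accept lung or any other site, with a different minimum number of cores for each. Section 3.1 describes the cohort D sample as one that follows radiation exposure. Section 9.1 plans a one-sample Wilcoxon signed rank test on paired differences, with no split by type of radiation or by field.

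**The concern.** The primary objective has a chemotherapy part and a radiation part. Cohort D is the only cohort whose required biopsy follows consolidation radiotherapy or PCI, so the radiation part rests on it. If some of its pairs come from tumour that no beam reached, those pairs have the same local exposure as cohort C pairs but carry a radiation label. Neither a positive nor a null cohort D result could then be attributed to irradiated tumour. The analysed group could also include patients outside the cohort that section 2.1 names.

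**Working it through.** **1. Can a PCI-only patient enter, and where?** Section 4.2 item 1 bars prior therapy in cohort A and more than one prior cycle in cohort B. Section 4.1 item 4 excludes candidates for thoracic radiotherapy or PCI from cohort C. Item 5 accepts completed PCI for cohort D. Under the eligibility criteria, a patient treated with 4-6 cycles and PCI can enter only cohort D. By section 2.1 that patient is not in cohort D.

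**2. Was the sampled tumour irradiated?**

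| Radiation received | Lesion biopsied | Exposure of that tumour |
|---|---|---|
| Thoracic, with or without PCI | inside thoracic field | chemotherapy + radiation |
| Thoracic, with or without PCI | outside any field | chemotherapy only |
| PCI only | extracranial, outside any other prior field | chemotherapy only |

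All three rows are permitted. Section 1.1.1 links thoracic consolidation to good response with minimal extra-thoracic disease, and item 5 requires no progression. These probably make the second row less common but do not exclude it.

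**3. The plan's own power figure.** Inputs from section 9.1: 12 analysable pairs, mean difference 10 points against 0, effect size 1.0, two-sided 0.05. The implied SD is 10 / 1.0 = 10 points. A one-sample t test with noncentrality 1.0 × √12 = 3.46 gives 88.3%. The signed rank test with an uncorrected normal approximation gives 87.4%, and the exact test (attained size 0.0425) about 85%. The stated 88% is reproduced and belongs to 12 pairs.

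**4. What pooling does.** Let k of the 12 pairs be un-irradiated. The mean change is

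[(12 − k) × irradiated shift + k × un-irradiated shift] / 12.

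Section 9.1 gives one planning shift, 10 points, for all paired comparisons. These include cohorts B and C, whose new biopsies follow chemotherapy without consolidation radiation. Putting 10 in both places gives 10 for every k, so there is no power loss on the plan's terms.

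The interpretation is still open. As an assumed illustration, a pooled mean of 7.5 points fits 12 pairs that all shift 7.5. It also fits 9 irradiated pairs that shift 10 with 3 un-irradiated pairs that shift 0: (9 × 10 + 3 × 0) / 12 = 7.5. The planned analysis cannot tell these apart.

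**5. Precision of a split.** With normal differences and SD 10, the half-width of the 95% CI is t(0.975, n − 1) × 10 / √n:

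- n = 12: 2.201 × 10 / 3.464 = 6.4 points
- n = 9: 2.306 × 10 / 3 = 7.7 points
- n = 6: 2.571 × 10 / 2.449 = 10.5 points

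**The case against.** The operative sections agree on who enters cohort D, and only section 2.1 and the schema differ, so enrolment is not in doubt. The objective speaks of change following chemotherapy and radiation in cohorts of patients. The first hypothesis in section 9 is worded as chemotherapy and/or radiation, and no sentence promises an estimate for irradiated tissue. Section 1.6 allows that tumour lysis may activate immunity, so radiation could act beyond its field. Prior radiation is reviewed (section 6.5.1) and listed in the section 7 calendar, and biopsy site must be known to apply the core minimum. Field status might therefore be reconstructed later. Section 9.1 already warns that post-treatment tissue may be scant.

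Much of this stands. The test is valid for change after standard therapy, PCI-only patients can be counted, and any split will be small. The case report form is not in the documents, so it cannot be said to omit the field item; the protocol simply lists none. The objection does not remove the mismatch with section 2.1, and a split made afterwards would be post hoc.

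A reader might also infer a large power loss. If un-irradiated pairs did not shift at all, exact power would fall from 85% to 53% with 3 such pairs of 12 and to 23% with 6. The documents do not support that reading. Both counts are assumed, and a zero shift after 4-6 chemotherapy cycles contradicts the common 10-point shift in section 9.1.

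**Conclusion.** The contradiction is real and bears on the primary endpoint. Section 2.1 and the schema require thoracic radiation, while five other places admit PCI alone. The free choice of biopsy lesion extends the problem to patients who did have thoracic radiation. As planned, the cohort D result answers how PD-L1 changed after standard therapy. It does not answer how PD-L1 changed in irradiated tumour.

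The extent cannot be sized, because the documents give neither the PCI-only share nor the mix of biopsy sites. The conclusion rests on the permitted routes in the eligibility and biopsy text and on the absence of a planned split. It does not rest on any assumed effect of radiation. It would be wrong to infer that the paired test is invalid, that its power is compromised, or that PCI-only patients are wrongly enrolled. Which definition is clinically right is not for this review to say.

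**What to change.** 1. Reconcile section 2.1 and the schema with the synopsis (Rationale and Treatment Plan), section 4.1 item 5, section 5.3 and section 9. Then align sections 1.6, 3.1 and the introduction to section 4 with the result.
2. For each new cohort D biopsy, record the site and whether the lesion lay inside the consolidation thoracic field, inside another prior radiation field, or in no field. The middle category is needed because section 4.2 item 5 permits other earlier radiation.
3. Add to section 9.1:

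> The cohort D paired change in PD-L1 is reported for all pairs (primary). It is also reported descriptively, as the Hodges-Lehmann estimate with 95% CI and no separate test, for pairs from a lesion inside the consolidation thoracic field and for all other pairs, with PCI-only pairs identified.

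4. State that in-field pairs reflect chemotherapy plus radiation and do not isolate radiation.

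The cost is one data item for up to 15 participants, a short paragraph and the text alignment. No new biopsies or patients are needed. The drawback is small subsets. With 5 pairs or fewer, an exact signed rank interval cannot reach 95%, since the smallest two-sided p value is 2 / 2⁵ = 0.0625. Individual changes should then be listed instead. The all-pairs result is kept, so nothing now planned is lost.

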4.4 Subject Recruitment

Target Enrollment for this study is 60 patients. Each cohort will consist of 15 patients. The inclusion and exclusion criteria in this study should not have a negative effect on the enrollment of these populations.

Patients will be recruited from physicians at the NYULMC Perlmutter Cancer Center (PCC). Consenting, screening, and treatment take place at the NYULMC PCC under the supervision of the Overall PI. Prospective subjects receive detailed information about this study its investigational nature, required study procedures, alternative treatments, risks and potential benefits of the study. They also receive the informed consent document to read. All questions are answered by the Principal Investigator.

The Principal Investigator will:

1. Obtain signed and dated informed consent from the potential subject before any study specific procedures are performed.
2. Determine patient eligibility See Section 4.1 and Section 4.2
3. Submit registration to NYULMC Perlmutter Cancer Center CTO
4. Receive registration confirmation from the Research Coordinator at NYU Perlmutter Cancer Center CTO, including a unique study identification number assigned to the patient by the research coordinator, which will be distributed to the study team upon registration.

Recruitment and consenting will take place in a private area such as an exam room to protect the patient's privacy. The informed consent process and documentation follows the established procedures of the NYULMC PCC CTO.

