4.5 Registration Procedures

4.5.1. General Guidelines

Each patient must sign and date an informed consent form before undergoing any study specific procedure unless a procedure is being performed as part of the patient's standard of care.

Enrollment in the study requires that all inclusion and exclusion criteria have been met. Enrollment occurs upon confirmation of registration from the NYULMC PCC Clinical Trials Office. The following materials must be submitted to the Research Coordinator for registration:

1. Complete signed and dated informed consent form
2. Complete signed and dated informed consent checklist
3. Complete signed and dated eligibility checklist
4. All supporting documentation verifying each criterion has been met

Registration will occur within 24 hours of research coordinator receipt of all of the above documents. A written confirmation of enrollment including a unique study identification number assigned by the research coordinator will be distinguished to the study team upon registration.

Pretreatment evaluation will therefore be as directed by standard clinical practice. Eligible subjects will be entered on study by the study coordinator.

All patients will be required to sign a written informed consent prior to being registered on this study. Every effort will be made to answer questions raised by patients and their families or advocates regarding the protocol and alternative therapies prior to asking a patient to sign the consent form.

Once eligibility is verified, a unique patient study number will be issued within 24 hours of receiving all required registration material. The patient will not be identified by name. This is the point, at which, the patient is considered on study. Subjects must not start any protocol procedures prior to registration.

Issues that would cause treatment delays should be discussed with the Overall Principal Investigator.

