5.10.2 Contraception

Pembrolizumab may have adverse effects on a fetus in utero. Furthermore, it is not known if pembrolizumab has transient adverse effects on the composition of sperm. Non-pregnant, non-breast-feeding women may be enrolled if they are willing to use 2 methods of birth control or are considered highly unlikely to conceive. Highly unlikely to conceive is defined as 1) surgically sterilized, or 2) postmenopausal (a woman who is ≥ 45 years of age and has not had menses for greater than 1 year will be considered postmenopausal), or 3) not heterosexually active for the duration of the study. The two birth control methods can be either two barrier methods or a barrier method plus a hormonal method to prevent pregnancy. Subjects should start using birth control from study Visit 1 throughout the study period up to 120 days after the last dose of study therapy.

The following are considered adequate barrier methods of contraception: diaphragm, condom (by the partner), copper intrauterine device, sponge, or spermicide. Appropriate hormonal contraceptives will include any registered and marketed contraceptive agent that contains an estrogen and/or a progestational agent (including oral, subcutaneous, intrauterine, or intramuscular agents).

Subjects should be informed that taking the study medication may involve unknown risks to the fetus (unborn baby) if pregnancy were to occur during the study. In order to participate in the study they must adhere to the contraception requirement (described above) for the duration of the study and during the follow-up period defined in section 10.2.2-Reporting of Pregnancy and Lactation to the Sponsor and to Merck. If there is any question that a subject will not reliably comply with the requirements for contraception, that subject should not be entered into the study.

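### At first enrolment, 4.1 item 13 accepts one contraceptive method for women of childbearing potential, while 5.10.2 makes two a condition of enrolment; the sections that sites are sent to for eligibility do not mention the second rule.

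*Combined protocol and SAP*

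**What the plan says.** **Section 4.1, item 13** applies to women of childbearing potential and to men. It requires "adequate contraception (hormonal or barrier method of birth control; abstinence") or surgical sterility, before study entry and while on study. It gives as reasons that the fetal effects of pembrolizumab are unknown and that the chemotherapy and radiation are teratogenic.

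**Section 5.10.2** sets its own enrolment condition for those who are neither pregnant nor nursing: "women may be enrolled if they are willing to use 2 methods of birth control or are considered highly unlikely to conceive". It then says what counts: "The two birth control methods can be either two barrier methods or a barrier method plus a hormonal method". Women who are surgically sterilised, postmenopausal or not heterosexually active are exempt. The requirement runs to 120 days after the last dose. Adherence is a condition of taking part, and the section ends firmly: "If there is any question that a subject will not reliably comply with the requirements for contraception, that subject should not be entered".

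**Section 4.4** lists the investigator's tasks, among them: "Determine patient eligibility See Section 4.1 and Section 4.2". **Section 4.5.1** adds: "Enrollment in the study requires that all inclusion and exclusion criteria have been met". It also requires a signed eligibility checklist and documents verifying each criterion.

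**Section 6.6.9.6**, which covers retreatment only, asks women of childbearing potential for two methods, surgical sterility or abstinence, and refers to 5.10.2.

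**The concern.** Two enrolment rules in the current text give different answers for the same woman, and the weaker one sits where sites are told to look. Contraception criteria exist here to prevent fetal exposure to agents that the protocol itself calls teratogenic, and to an antibody that 5.10.2 says may harm a fetus. If a site applies item 13 as written, a woman on one method can be registered although 5.10.2 says that she should not be. That is a lower standard of protection than the protocol intends, and an avoidable eligibility deviation.

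The retreatment criteria suggest that two methods is the intended rule throughout. The documents give no reason why a woman starting platinum, etoposide and pembrolizumab should face a weaker rule than one returning for pembrolizumab alone.

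**Working it through.** No sample size, power or error rate is involved, so the check is a comparison of the provisions. Take a woman who is not surgically sterile, not postmenopausal and heterosexually active.

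| Place | Governs | Methods required of her | Refers to 5.10.2? |
|---|---|---|---|
| 4.1 item 13 | First enrolment | 1 (hormonal or barrier) | No |
| 4.2 item 17 | First enrolment (exclusion) | No number stated | No |
| 5.10.2 | Enrolment and participation | 2 | Not applicable |
| 6.6.9.6 | Retreatment | 2 | Yes |

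Step 1. Suppose that she uses a hormonal method alone. Item 13 joins hormonal and barrier with *or* and uses the singular, so she meets it. The same holds for one barrier method alone.

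Step 2. Apply 4.2. Item 17 excludes women who are pregnant, breast-feeding or expecting to conceive. It says nothing about how many methods are needed, so it does not stop her.

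Step 3. Apply 4.4 and 4.5.1. Eligibility is decided from 4.1 and 4.2, and all inclusion and exclusion criteria must be met. She meets them. Section 6.2 also asks only for a review of the inclusion and exclusion criteria.

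Step 4. Apply 5.10.2. She has one method, and neither permitted pair (two barriers, or a barrier with a hormonal method) is satisfied. She is not in an exempt group, so she may not be enrolled.

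Step 5. Test the limits of the conflict. Abstinent and surgically sterile women are accepted by both sections. Women already using a permitted pair are also accepted by both. Men are outside the two-method rule. At retreatment 6.6.9.6 already asks for two methods, so the conflict is confined to first enrolment.

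**The case against.** The strongest reply is that the documents already settle the matter. Section 5.10.2 is itself an enrolment rule and does not read as advice. A general criterion and a stricter specific one can both be obeyed by following the stricter. Item 13 never says in terms that one method is sufficient, and the eligibility checklist, which sites would actually use, is not shown. Exclusion 17, pregnancy testing and withdrawal on pregnancy remain as safeguards.

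Much of this stands. A reader might infer that the protocol authorises enrolment on one method, or that sites will in practice enrol such women. The documents support neither: 5.10.2 forbids it, and whether the checklist repeats item 13 or 5.10.2 cannot be seen. What the reply does not answer is that the eligibility instruction in 4.4 leads only to the weaker text. The other safeguards set no number of methods, and testing detects a pregnancy rather than preventing one.

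Three further inferences are tempting and should be resisted.

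- *A sponge or spermicide alone would satisfy item 13.* Section 4.1 lists no barrier methods. The list ("diaphragm, condom (by the partner), copper intrauterine device, sponge, or spermicide") is in 5.10.2, so a site using it is reading the very section that demands two methods.
- *The definition of childbearing potential lets fertile women through.* Item 13 and 6.6.9.6 each join two conditions with *or*, so each counts every woman who is not surgically sterilised. They therefore take in unsterilised postmenopausal women, whom 5.10.2 exempts (aged at least 45, and "has not had menses for greater than 1 year will be considered postmenopausal"). That is over-inclusion and misses no fertile woman.
- *Item 13 leaves the 120 days after the last dose uncovered.* Section 5.10.2 covers that period, and exclusion 17 runs to the same point, so there is no separate gap.

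**Conclusion.** The inconsistency is real and is in the current text. Item 13 asks for one method and 5.10.2 for two, and the eligibility instruction leads to item 13 without any pointer to 5.10.2. Because 5.10.2 is the stricter rule and already binds, the defect is the risk that a check built on 4.1 and 4.2 applies the weaker fetal-safety rule.

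The group at risk is women of childbearing potential who are heterosexually active and rely on a single method at first enrolment. The documents give no count; that it is likely small is a judgement. The conclusion rests on reading item 13's singular wording as satisfied by one method, which is its plain meaning, and on sites following 4.4 as written. Sample size, power and analysis are untouched. The correction is worth making because it concerns patient and fetal safety and costs almost nothing.

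**What to change.** Amend item 13 of Section 4.1 so that women and men are treated separately. For women of childbearing potential: *must agree to use two methods of birth control as specified in Section 5.10.2, for the period stated there (through 120 days after the last dose of study therapy), or be abstinent or surgically sterile.* For men, keep the present wording, so that adequate contraception stays defined for item 14, which does not change. Update the eligibility checklist if it mirrors item 13.

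Leave the definition of childbearing potential in 4.1 and 6.6.9.6 alone. Table 5 limits pregnancy testing to women of childbearing potential, so a narrower definition would shrink the tested group and correct no failure to protect. The reference to 5.10.2 also shows sites its exemption for postmenopausal women.

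The cost is one amended criterion and possibly one checklist line, with no change to treatment, visits, pregnancy testing or analysis.
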